## 1.3 AIMS OF THE TRIAL

**Aim 1: Integrate clinical guidelines for adults with SCD into our beta version of iManage, an mHealth app.** Three focus groups will include a total of fifteen adults with SCD to identify user needs and preferences for the guidelines and app. This information will be used to adapt iManage which will then be tested and iteratively refined through usability sessions with 10 adults until ease of use and usefulness are high.

**Aim 2: Evaluate the feasibility and acceptability of the refined iManage in a pilot study with adults with SCD.** We will recruit 50 adults from the population of adults with SCD at the Vanderbilt Meharry Sickle Cell Disease Center of Excellence and Ohio State Sickle Cell Center for a 6-month pilot study to evaluate usability, acceptance, and usage. At the end of the study, we will conduct interviews with a subset of participants to gain an in-depth understanding of usage patterns and how

to sustain engagement to promote ongoing iManage use.

**Aim 3: Evaluate the efficacy of the refined iManage app on SCD-specific knowledge.** We will test the hypothesis that the refined iManage will increase SCD-specific knowledge by measuring SCD-specific knowledge at the start and end of the 6-month pilot study. We will conduct exploratory analyses of secondary outcomes including patient activation, adherence to guidelines, missed days of school/work, and self-efficacy.

*Specific Aim 1:*

Outcomes: The primary outcome of step 1 will be themes from focus groups that will be utilized to refine the Beta version of iManage in step 2. Outcomes from step 2 will include usability data from the System Usability Score, as well as quantitative and qualitative data about task completion.

*Specific Aim 2:*

Rationale: Technological interventions can only be successful at changing outcomes if they are feasible and acceptable. Through measurement of usability, acceptance, and usage, we can discover patterns that can lead to insights about how to modify technology to have a larger impact and reach.

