Outcomes: We will measure usability and acceptability of iManage through surveys at the 6 month follow up, and we will measure usage of iManage throughout the 6-month period. Usability will be measured by the widely used and validated System Usability Scale. We will measure acceptability with a validated survey instrument based on the technology acceptance model introduced by Gao et al. The mobile health application for the guidelines has built-in tracking of the number of times the application is launched, how many times each of the functions are used, and how many times each button has been pushed. To measure usage, we will record the numbers of each of these events for each adult. In addition to total use, we will measure usage over time including any use, initial use, periodic use, and sustained use. We will also use a satisfaction/acceptability questionnaire to help evaluate acceptability of the app.

*Specific Aim 3:*

Rationale: Currently, health care providers provide education about SCD at clinic visits yet, data show that technology solutions designed to improve SCD knowledge are effective. We hypothesize that delivering NHLBI SCD-guidelines via an mHealth app, iManage, will increase patients' SCD-specific knowledge

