These will be the same as the usability sessions in the original protocol and consent, however, we may need to recruit additional participants for the usability sessions with the updated app for 1 to 2 rounds, requiring an additional 10 participants who may need to be recruited, increasing total recruitment for this study to 85. All the usability questions, recruitment, and consent will be the same as the prior questions.

*Specific Aim 2 & 3:*

Participants will participate in two visits, an initial visit where participants will complete the surveys shown in Table 1, where the participant will be randomized into control arm or intervention arm (1:1 ratio), and if in the intervention arm, the research team will introduce and demonstrate the iManage app. At a 6-month follow up visit, surveys will be repeated, and the research team will conduct a semi-structured interview about what they liked about the mHealth app, what they didn't like, what barriers they had to using the app, how the mHealth app could be improved, and an example of when the app helped them with care of their SCD. Interviews will take place either in person or remotely via phone or web meeting service (such as GoToMeeting). When conducting remote interviews, we will record audio using software such as GoTo Meeting or Skype. All recording files will be saved to an encrypted drive, which can only be accessed by study team members. Once a file has been removed from the secured recording media and stored on the encrypted drive, it will be deleted from the recording media.

KSP trained in human subjects research will obtain consent and administer the surveys and interview. A member of the KSP will set up and instruct the participant on how to access the mHealth app on their mobile phone, how to login to the intervention using his/her unique study identifier. The KSP will provide a 10-minute demonstration of the mHealth app, and have the participant interact with the app as independently as possible for 10 minutes to complete assisted tasks to gain knowledge and confidence to take action independently. KSP will be available to assist with questions. Participants may also get emails periodically throughout the study to ask them if they have questions about the study or the guidelines.

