**PHASE II Pilot Feasibility Randomized Controlled Trial****(30 months)**

Fifty participants will be enrolled or a 6-month pilot study where they will be randomized to one of two arms, standard care (control arm), or receiving iManage that will include interactive content and a fully searchable collection of the SCD-specific guidelines that are age- and health literacy-appropriate (intervention arm). An equal number of participants will be in each of the two arms (25 in each arm). They will participate in an initial visit and a 6-month follow up visit.

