**3.0 EVALUATIONS****3.1 Patient Evaluations**

Participants will provide written informed consent on paper or through REDCap e-consent and sign an authorization to use or disclose personal health information (PHI) form. Participants will get a \$250 check or gift card if they are in the 4-hour focus groups and a \$100 check or gift card if they are in the 90-minute usability session. For the pilot study, they will be compensated with a \$25 gift card for their initial visit and \$50 for their 6-month follow up visit. Both visits should take about 60 minutes. All checks or gift cards will be mailed or sent electronically. During the initial visit, participants will complete surveys, and if randomized to the intervention arm, the research team will introduce and demonstrate the iManage app. At a 6-month follow up visit, surveys will be repeated, and the research team will conduct a semi-structured interview about what they liked about the mHealth app, what they didn't like, what barriers they had to using the app, how the mHealth app could be improved, and an example of when the app helped them with care of their SCD. KSP trained in human subjects research will obtain consent and administer the surveys and interview. All survey instruments will be available in electronic form (through Research Electronic Data Capture, or

REDCap) and administered via iPads. Paper forms will also be available, and KSP will be available to answer questions. The interview will be audio recorded, transcribed, and de-identified for analysis.

Table 1 Time when each activity will be completed, and time to complete each activity			
Activity or Measure	Initial visit	6-month follow up	Time (mins)
Enrollment/Consent	X		20
Demographics	X		5
Demonstration of iManage	X		20
SCD-specific knowledge	X	X	5
SCD Specific Self Efficacy Assessment 	X	X	5
Patient Reported Outcomes Measurement Information System (PROMIS) measures	X	X	10
Patient Activation Measure 	X	X	5
Adherence to guideline measurements	X	X	5
Patient-centered Outcomes Questionnaire 	X	X	5
PHQ-9	X	X	1
REALM-SF	X	X	3
Medication adherence (Visual Analogue Scale (VAS) (1 item) and modified Morisky Scale (8 items))	X	X	1
Barriers to care	X		3
iManage usage and usability Satisfaction/acceptability questionnaire (11 items)		X	10
Semi-structured interview		X	30
Compensation	\$25	\$50	

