#### **Aim 2&3:**

Descriptive statistical analyses will be conducted to characterize and highlight unique aspects of this population. The statistics used to summarize the responses to the various instruments and their scales will be based on standard and recommended practice. Frequencies and percentages will be used for categorical data, means and standard deviations for continuous measures that are normally distributed, and the median and inter-quartile range for continuous measures that are skewed or otherwise not normal. To examine relationships between measures, crosstab tables with chi-square will be used for categorical variables, a t-test or ANOVA for a categorical and continuous variable (or the equivalent non-parametric test), and a Pearson correlation or Spearman rank correlation as appropriate for the association between two continuous measures. Interview data gathered during the visits will be transcribed and de-identified as described in aim 1. We will use a combined inductive-deductive approach, which will be informed by knowledge of SCD, design of usable apps, and social science theory.

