#### **Aim 2&3:**

As the primary outcome of this aim is the change in SCD-specific knowledge, we calculated the power for our sample size of 50 participants based on improvements in SCD-specific knowledge from preliminary data from St. Jude and a study that used a private online computer network within the hospital. These studies showed an improvement of about 10-20% in test scores for SCD-specific knowledge, with a baseline mean score of around 7.5 and standard deviation of about 2.5. If we use an improvement of 15%, and assume a baseline score of 7.5, our target sample size of 50 achieves 86.2% power to detect a mean of paired differences of 1.1 with an estimated standard deviation of paired differences of 2.5, at a significance level (alpha) of 0.05 using a two-sided paired t-test.

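### The primary analysis of knowledge never names iManage against standard care, and the stated 86.2% power belongs to a before-after test on all 50 participants, not to the randomised comparison

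*Combined protocol and SAP*

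**What the plan says.** **Design.** Section 2.2 (Phase II) states that "they will be randomized to one of two arms, standard care (control arm), or receiving iManage", with 25 in each arm. Section 2.1 (Aims 2 and 3) says the same: "the participant will be randomized into control arm or intervention arm (1:1 ratio").

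**Aim and outcome.** Aim 3 in section 1.3 is to "Evaluate the efficacy of the refined iManage app on SCD-specific knowledge". Sections 1.3 and 3.2 define the primary outcome as the change in knowledge from the initial visit to 6 months. Neither states a contrast between arms.

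**Analysis.** Section 4.1 (Aims 2 and 3) describes summary statistics and then a general list of tests for relationships between measures. The list includes "a t-test or ANOVA for a categorical and continuous variable (or the equivalent non-parametric test"). It mentions neither knowledge nor randomised arm, and it does not identify a primary analysis.

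**Power.** Section 4.2 (Aims 2 and 3) says that "our target sample size of 50 achieves 86.2% power to detect a mean of paired differences of 1.1", with an SD of the paired differences of 2.5, "at a significance level (alpha) of 0.05 using a two-sided paired t-test". The 1.1 points come from a 15% improvement on a baseline mean of 7.5. The earlier studies are said to show improvements of about 10-20%.

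**The concern.** The control arm exists so that Aim 3 can be answered by comparing iManage with standard care. Only that contrast is protected by randomisation, and the plan leaves it unnamed. The one test attached to knowledge ignores arm.

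If that paired test became the primary analysis, it could mislead in two ways:

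- **Positive with no app effect.** Knowledge can rise in both arms. The same instrument is given twice (section 3.1: "At a 6-month follow up visit, surveys will be repeated"), and standard care already includes teaching (section 1.3: "Currently, health care providers provide education about SCD at clinic visits"). A before-after test attributes any such rise to the app.
- **Negative with a real app effect.** Pooling mixes 25 people who have the app with 25 who do not, so the average change is diluted.

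If the paired test was meant only for sample size, no primary analysis is specified. Pooled or between-arm, final score or change, adjusted or not, would all remain open after the data are seen. On either reading, the only power figure offered for the primary outcome does not describe the trial's comparison.

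**Working it through.** **Inputs from the plan**

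- 25 per arm (2.2)
- mean difference δ = 1.1, SD of change 2.5, baseline mean 7.5, baseline SD about 2.5, two-sided α = 0.05 (4.2)

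**Assumptions added here**

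- no dropout
- no gain on standard care when power is computed
- r, the correlation between the two visits, is not given. If the SD is 2.5 at both visits and also for change, then 2.5² = 2 × 2.5² × (1 − r), so r = 0.5.

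All powers use the noncentral t distribution with noncentrality λ.

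**1. The plan's own figure.** Paired test, n = 50: λ = (1.1/2.5) × √50 = 3.11, df = 49. Power = **86.2%**, as stated.

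**2. The same inputs applied to the two-arm trial**

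| Analysis | λ | df | Power |
|---|---|---|---|
| Change between arms, 25 v 25 | 1.1 / (2.5 × √(2/25)) = 1.1/0.707 = 1.56 | 48 | **33%** |
| ANCOVA, r = 0.5; residual SD 2.5 × √(1 − 0.25) = 2.165 | 1.1 / (2.165 × √(2/25)) = 1.1/0.612 = 1.80 | 47 | **42%** |
| Paired test, iManage arm only, n = 25 | (1.1/2.5) × √25 = 2.20 | 24 | 56% |
| Paired test, all 50, only iManage gains: mean 0.55, SD √(2.5² + 0.55²) = 2.56 | (0.55/2.56) × √50 = 1.52 | 49 | 32% |

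None of these recovers 86.2%. Over the plan's 10-20% range (0.75 to 1.5 points), power for change between arms runs from 18% to 55%.

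**3. Sensitivity to r**

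| Held fixed | r | Change | ANCOVA |
|---|---|---|---|
| SD 2.5 at each visit | 0.3 | 25% | 36% |
| SD 2.5 at each visit | 0.7 | 50% | 57% |
| SD of change 2.5 | 0.3 | 33% | 47% |
| SD of change 2.5 | 0.7 | 33% | 38% |

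The 33% for change needs no value of r, because 4.2 gives the SD of change directly.

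**4. What 25 per arm can show**

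- Difference detectable with 80% power: 2.02 points on change (2.02/7.5 = 27%), or 1.75 with ANCOVA at r = 0.5 (23%).
- Expected 95% CI half-width: 2.01 × 0.707 = 1.42 points on change; 2.01 × 0.612 = 1.23 with ANCOVA at r = 0.5.
- Size needed for 80% power at 1.1 points: 83 per arm on change, 62 with ANCOVA at r = 0.5.

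**5. If the paired test were the analysis and the app did nothing.** The plan gives no expected gain on standard care, so the gains below are assumed, equal in both arms, with SD of change 2.5. The table shows how often the test is significantly positive.

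| Gain in both arms | Pooled, n = 50 | iManage arm only, n = 25 |
|---|---|---|
| 0 | 2.5% | 2.5% |
| 0.25 | 10% | 7% |
| 0.5 | 28% | 16% |
| 0.75 | 55% | 30% |

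In a simulation of 20,000 trials with r = 0.5, the pooled test was positive in 10%, 29% and 55% of trials for gains of 0.25, 0.5 and 0.75. The between-arm tests rejected in about 5% throughout.

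**The case against.** **It is a pilot.** Section 2.2 calls Phase II a pilot feasibility trial, and Aim 2 concerns feasibility and acceptability, so low between-arm power is not in itself a fault. That stands, and no larger trial is asked for. But Aim 3 is stated as efficacy, and 4.2 supports it with 86.2% power.

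**The paired test is only in the sample-size section.** Section 4.1 does list a t-test for a categorical and a continuous variable, which could be applied to arm and change. This is fair: the fault in 4.1 is under-specification rather than a declared wrong test. The false-positive and dilution figures therefore apply only if the paired test is used, and the false-positive ones also rest on assumed gains. The generic list still does not name the contrast, and it does nothing to rescue the 86.2%.

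**The 86.2% is correctly labelled.** Section 4.2 says plainly that it refers to paired differences. That is also true; the arithmetic is right and the design it describes is wrong.

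**Baseline is already used.** Because the outcome is change, each participant's baseline is subtracted. What is missing is adjustment for it as a covariate. That is a gain in precision; a two-sample comparison of change would also be valid.

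**The ANCOVA figures depend on r.** They do. With visit SDs of 2.5 and r = 0.7, the detectable difference is 1.44 points (19% of 7.5), inside the plan's range, and 43 per arm would give 80% power at 1.1 points. At 25 per arm, power for 1.1 points is still 57%, well short of 86.2%.

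**Conclusion.** The concern holds. No section names iManage against standard care as the comparison for knowledge, and the stated power is for a one-sample before-after test in which all 50 participants gain 1.1 points.

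The firmest figure is 33% power for change between arms, which uses only the plan's own inputs plus two favourable assumptions: no dropout and no gain on standard care. ANCOVA gives 42% at r = 0.5. Across r = 0.3 to 0.7, under either way of fixing the SDs, between-arm power runs from 25% to 57%. Dropout lowers it further; 20 completers per arm would give 27% on change.

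This must be corrected before analysis, because it concerns the primary efficacy inference and the only power claim made for it. The need is to name the contrast and restate the power; small size is acceptable in a pilot that reports an estimate.

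**What to change.** **Section 4.1.** Add: *Primary analysis: 6-month SCD-specific knowledge compared between randomised arms by ANCOVA adjusted for baseline knowledge, all participants analysed in their assigned arm; adjusted mean difference with 95% CI.* Make within-arm paired changes descriptive. This is compatible with the existing change outcome, since ANCOVA on the 6-month score or on change gives the same arm effect.

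**Section 4.2.** Replace the 86.2% with between-arm power at 25 per arm: about 33% on change, and about 42% with ANCOVA at r = 0.5, with r labelled as an assumption. Give the expected 95% CI half-width (about 1.4 points on change, 1.2 with ANCOVA) and describe the efficacy result as a pilot estimate.

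**Sections 1.3 and 3.2.** Add the arm contrast to the Aim 3 hypothesis and the primary outcome, so that they match 4.1.

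**Section 4.3.** State how the missing-data approach applies to the primary model, so that analysis by assigned arm is well defined.

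**Cost.** Wording and one regression model. Knowledge is already measured at both visits, so no new data are needed. The real price is that stated power falls from 86.2% to about 33-42%. Restoring 80% for 1.1 points would take about 83 per arm on change or about 62 with ANCOVA at r = 0.5, so with 50 participants the efficacy aim has to be presented as estimation.

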### **4.3 Data Integrity, Management, and Missing Data**

This project will utilize the REDCap platform for data collection and management. Data will be manually retrieved from the EHR and entered into REDCap.

This study will utilize REDCap (Research Electronic Data Capture), a software toolset and workflow methodology for electronic collection and management of clinical and research data, to collect and store data. The OSU Center for Clinical and Translational Science (CCTS) Research Informatics Services will be used as a central location for data processing and management. REDCap provides a secure, web-based application that provides an intuitive data manipulation interface, custom reporting capabilities, audit trail functionality, real-time data monitoring/querying of participant records, and variations of data exporting/importing. REDCap is hosted by OSUWMC IT in the Ackerman Datacenter ([name]). The OSU REDCap instance is located on internal

OSUWMC network. Remote access to this network can be obtained over an encrypted VPN tunnel (AnyConnect) This VPN uses Protocol: DTLS and Cipher: RSA\_AES\_128\_SHA1. Background checks are performed on all staff that are on the network or obtaining VPN access.

We will take the following steps to ensure rigor and reproducibility of this study. Data will be de-identified, and survey responses will be securely stored in REDCap or both a password protected computer and external hard drive. A standard analysis file will be created for use in the analysis of the trial for manuscripts and reports. The analysis file will include data from screening and baseline forms, treatment forms, mHealth application data, and outcomes. First and foremost, we plan to minimize the amount of missing data through various strategies. However, in the case of missing data, randomness of missing data will be assessed and when feasible, imputation will be performed. We will minimize nonadherence and attrition by employing retention strategies and adequate follow-up of all participants (e.g. contact from study coordinator; increasing reimbursement over time for study participation). We will employ techniques to ensure self-administered survey completion by requiring needed questions in REDCap so a participant cannot submit a final survey without answering each question, and by following up on incomplete surveys through telephone contact and possibly completing the survey over the telephone.

## **5.0 DATA MONITORING**

The local principal investigator and/or members of the research team will monitor the study for inclusion/ exclusion criteria, accrual/withdrawal rates, and breech of confidentiality annually prior to submission to the IRB. Any adverse events will be reviewed immediately with the Principal Investigator and will be reported to the Ohio State IRB per IRB regulations. All study events will be summarized once a year for the IRB, during the annual continuing review reporting.

## **6.0 REGISTRATION AND STUDY ORGANIZATION**

Approval for use of this protocol and consent forms by the Institutional Review Board (IRB) must be obtained prior to patient participation on the trial. All reasonable measures will be taken to protect the confidentiality and identity of the patient and patient's records according to State and Federal laws. Patient identity will not be revealed in any publication.

The parent/legal guardian of each patient will be given consent forms to read and sign on paper or through REDCap e-consent prior to the patient's entry into the trial, if eligible. These forms will contain a description of the objectives of the trial, a description of the examinations and tests which will be given to the patient as each part of the trial, as well as expectations of the patient as a trial participant. These consent forms will be given to the patient by a KSP.

## **8.0 APPENDICES**

None
